2.2 STUDY DESIGN

This study is a monocentric prospective interventional study on 250 subjects (150 patients and 100 controls). The promotor of this study is the Cliniques universitaires Saint-Luc (Brussels, Belgium).

2.2.1 Study population

This study will be performed in 150 subjects with confirmed or suspected telomeropathy and recruited through Cliniques universitaires Saint-Luc (CUSL) (Brussels, Belgium).

We will include patients with suspicion of telomeropathy: patients with idiopathic pulmonary fibrosis, adult or pediatric medullar dysplasia or myelodysplasia, unexplained liver cirrhosis or unexplained liver regenerative nodular hyperplasia.

100 age-matched healthy controls will be recruited from CUSL.

2.2.2 Study endpoints

Endpoint #1: To assess the suitability of nasal brushing analyses and blood tests for the diagnosis of telomeropathies.

Rationale

To date, the complete diagnosis of telomeropathies, including the identification of responsible mutations, is based on blood samples and fibroblast cultures obtained through skin biopsies. Cells obtained through nasal brushing offer the opportunity to detect mutations involved in telomeropathies, in a mildly invasive way. We will thus assess a population of patients with a suspicion of telomeropathy, using a combination of blood tests and nasal brushings, and will compare their nasal brushing results to those of age-matched healthy controls. If we confirm that the nasal brushing offers the opportunity to i) detect damaged telomeres and premature cellular senescence and ii) identify mutations related to telomeropathies, this technique could become a non-invasive clinical tool for the diagnosis work-up of telomeropathies

Assessments

We will collect blood samples in each patient and will perform a nasal brushing to each subject (patients and controls) included in this study. One sample of blood will be collected for each patient and processed following the protocol further described (see chapter 3.1.).

For nasal brushing, one collection will be performed in the most accessible nostril. We will evaluate if it is possible to detect damaged telomeres and premature cellular senescence in patient, in comparison to healthy controls.

In the patients group, collected cells will be split into three parts, two will be devoted to Endpoint#1, and the other for the Endpoint #2, following the protocol further described (see chapter 3.2.).

For patients recruited from the pediatric consultation, if possible, this sample will be collected during another medical procedure planned under general anesthesia (eg. marrow puncture). Similarly, pediatric controls will be recruited among patients undergoing elective otorhinolaryngological surgery (eg. grommets, tonsillectomy).

Endpoint #2: To develop primary cell cultures for the functional study of new germline mutations.

Rationale

To date, various germline mutations have already been identified in telomeropathy patients, in a total of 15 genes. Understanding how these mutations were affecting telomere biology relied on *in vitro* studies with either patient-derived fibroblasts or engineered human cell lines recapitulating the mutation. This was a mandatory step towards the molecular understanding of these pathologies. Because olfactory neural precursors have the capacity to grow in culture, this offers the additional possibility to perform functional studies on primary cultures of nasal brushing-derived cells for novel mutations, with still unknown impact on telomeres, that would be identified. Again, this could advantageously replace patients' fibroblast cultures.

Assessments

The second part of cells harvested from the olfactory epithelium will be cultured, according to protocol described in chapter 3.2.

Endpoint #3: To evaluate whether patients with telomeropathies have impaired olfactory function.

Rationale

Olfactory function is decreased in several diseases and is increasingly recognized as an indicator of biological aging. To date, no data exist regarding the impact of telomeropathies on olfactory function. Therefore, we aim to psychophysically assess olfactory function in patients with telomeropathies, in comparison to age-matched healthy controls. This study will be performed in a subset of subjects (see section 7.1).

Assessment

For each participant older than 6 years old, olfactory function will be assessed with the validated test.

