Telomeropathies are premature ageing diseases resulting from pathogenic germline mutations in telomere biology-related genes. Most telomeropathy patients have telomeres that are too short for their age. Telomere length (TL) can be measured in blood cells using a technique called Flow-FISH (FF) that combines fluorescent in situ hybridization (FISH) with flow cytometry (Baerlocher et al. 2006). To provide a diagnostic tool for telomeropathies in Belgium, the laboratory of [name], in collaboration with CUSL, recently implemented the FF technique and measured TL in a cohort of 491 healthy volunteers aged 0-99 years. In combination with FF, additional genetic and phenotypic studies on patients' cells are needed to tell whether the disease is caused by prematurely defective telomeres. Knowing this is important to i) exclude any other cause of the disease, ii) avoid the use of inappropriate treatments, iii) better manage the immunosuppressive regimens that are associated with hematopoietic stem cell or lung transplantation in some telomeropathy patients and iv) enable possible targeted therapies. For instance, while pulmonary fibrosis carriers with TOLLIP polymorphism may benefit from N-acetylcysteine treatment, those with defective telomeres may possibly benefit from Danazol, a telomerase-activating drug previously associated with increased TL in PBMCs and stability of lung function in idiopathic PF (IPF) patients (Townsley et al. 2016).

To date, mutations in 15 telomere biology-related genes have been linked to telomeropathies and include *TERC* and *TERT* telomerase core components, various chaperone genes with roles in *TERC* maturation and stability, shelterin complex genes, the CST complex with important function in telomere replication and *RTEL1* with multiple roles at telomeres, including replication (Savage 2018). There are however many patients with abnormally short telomeres and still unidentified mutation. On the other hand, in patients with *CTC1* or *POT1* mutations, presenting with severe telomeropathies, telomeres

are defective but not abnormally shortened (Gu et al. 2018), underlying the need to combine TL measurements with additional phenotypic and genetic analyses for the proper diagnosis of telomeropathies.

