One way to evaluate telomere dysfunction, independently of TL measurement in blood cells by FF, is to perform a combination of telomeric FISH and immunofluorescence (FISH/IF) against DNA damage markers to guantify the damaged telomeres, a conserved feature of cells from telomeropathy patients. The evaluation of cellular senescence, using the well-established Senescence-Associated β -Galactosidase (SA- β -Gal) assay (Dimri et al. 1995) is vet another assay to evaluate a premature ageing cellular phenotype. Importantly however, neither FISH/IF nor SA-β-Gal assays can be performed on blood cells. The cellular diagnosis therefore requires other cell types. Usually, a skin biopsy is performed that requires to establish a primary culture of fibroblasts for further analyses. The skin biopsy is however invasive, leaving permanent scars. A skin biopsy can also be used to identify the genetic mutations at the origin of the disease. This type of cell is usually preferred over blood cells because of the known ability of blood cells to undergo somatic genetic rescue that can offset the pathogenic effect of germline mutations (Revy et al. 2019). In this respect, although intragenic compensatory mutations are observed in blood cells from telomeropathy patients, in the majority of the cases, indirect somatic genetic rescue is obtained through the acquisition of well-defined activating point mutations in the promoter of hTERT gene that codes for the catalytic subunit of telomerase (Revy et al. 2019). Since this has already been observed in cases of heterozygous germline mutations in PARN, NHP2 or TERC genes (all involved in maturation and activity of telomerase), this suggests that the detection of these point mutations in blood cells may be a strong indicator of the existence of a telomeropathy, prior to the exome-seg analysis.

Importantly as well, having non-blood cells in culture, like fibroblasts, allows functional studies of the mutations to increase our knowledge of the telomeropathies at the cellular level.

Altogether, this underlines the interest of having access to non-blood cells from telomeropathy patients for proper diagnosis, mutation identification and functional studies. In that context, developing alternative and less invasive approaches to collect non-blood cells so as to replace skin biopsies would be highly beneficial to patients.

THE OLFACTORY EPITHELIUM: AN ALTERNATIVE SOURCE OF CELLS FOR TELOMEROPATHY DIAGNOSIS AND UNDERSTANDING?

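### Endpoint #1 compares nasal staining only between patients and healthy controls, so a positive result cannot by itself support its diagnostic use among suspected patients

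*Combined protocol and SAP*

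**What the plan says.** The Introduction (Telomeropathies: diagnosis) sets the clinical question. Blood Flow-FISH combined with further genetic and phenotypic studies "are needed to tell whether the disease is caused by prematurely defective telomeres", and the first listed reason for wanting to know is to "exclude any other cause of the disease". Section 2.1 and Endpoint #1 make suitability for diagnosis the aim.

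For the nasal staining, section 2.2.2 names one comparator, in two places. The rationale says that the investigators "will compare their nasal brushing results to those of age-matched healthy controls". The assessment says: "We will evaluate if it is possible to detect damaged telomeres and premature cellular senescence in patient, in comparison to healthy controls".

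The patient group is 150 people with confirmed or suspected telomeropathy (section 2.2.1), drawn from pulmonary fibrosis, marrow and liver clinics (section 4). Section 3.2 reserves control cells for the staining. Section 9 says where samples are processed and gives no contrast, accuracy measure or reference standard. The text does not define what makes a case confirmed.

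**The concern.** The patients differ from the healthy controls in two ways at once: some have a telomere disorder, and all have, or are suspected of having, a serious lung, marrow or liver disease, often with treatment. A higher staining score in patients fits either explanation, or both. In practice the stain would be used among suspected patients, to separate those whose disease comes from telomeres from those whose disease has another cause. The stated comparison does not address that separation.

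At stake is the first of the two conditions in the Endpoint #1 rationale, the detection of damaged telomeres and premature senescence. It could be met because patients are ill, and the result could then be read as evidence on diagnostic suitability.

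The point is limited to staining. Mutation detection, the second condition, is a separate read-out and is not criticised here.

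**Working it through.** **The plan's own figure.** Section 2.2 gives 150 + 100 = 250 subjects. The sum is consistent, but no alpha, power, effect size or SD is stated, so the sample size cannot be reproduced. Everything below is an illustration under assumptions: normal scores, SD 1, two-sided 5% test.

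**1. Could illness alone make the stated comparison positive?** Suppose there is no telomere effect and an illness-only shift of d SD in patients. The standard error is √(1/150 + 1/100) = 0.129, the noncentrality is d/0.129, and there are 248 degrees of freedom.

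| d (SD) | Noncentrality | Chance of significance |
|---|---|---|
| 0.1 | 0.77 | 12% |
| 0.2 | 1.55 | 34% |
| 0.3 | 2.32 | 64% |
| 0.4 | 3.10 | 87% |

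**2. Does the comparison tell the two explanations apart?** Take a mean patient–control difference of 0.5 SD (power about 97%).
- Signal only in true telomeropathy, 30% of patients affected: their shift is 0.5/0.3 = 1.67 SD, and the AUC among patients is Φ(1.67/√2) = 0.88.
- The same 0.5 SD shift in every ill patient, whatever the cause: the AUC among patients is 0.50.

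The mean difference is identical, and the diagnostic value is opposite.

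**3. What if a cut-off were set on healthy controls?** The documents propose none, so this is conditional. With 85% specificity in healthy controls the cut-off is z = 1.036. Specificity in unaffected patients is Φ(1.036 − d): 80%, 77% and 74% for d = 0.2, 0.3 and 0.4.

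**4. What could a contrast among patients deliver?** The affected share is not given. Wilson 95% intervals for two assumed splits of the 150:

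| Confirmed | Sensitivity | Specificity |
|---|---|---|
| 45 | 38/45 = 84% (71% to 92%) | 89/105 = 85% (77% to 90%) |
| 30 | 25/30 = 83% (66% to 93%) | 102/120 = 85% (78% to 90%) |

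**5. What does an imperfect reference cost?** The Introduction says that in some severe cases telomeres "are defective but not abnormally shortened", and also: "There are however many patients with abnormally short telomeres and still unidentified mutation". Suppose 45 true cases, true sensitivity 84% and specificity 85%, and no false-positive reference results. Missed cases then sit in the not-confirmed group, where only 16% of them are stain-negative:
- 40 found: (105 × 0.85 + 5 × 0.16)/110 = 82% apparent specificity.
- 31 found: (105 × 0.85 + 14 × 0.16)/119 = 77%.

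A contrast among patients therefore gives evidence on specificity but does not settle it.

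**The case against.** **The protocol asks less of staining than this implies.** The Introduction gives the diagnostic question to Flow-FISH, genetics and phenotype together. Endpoint #1 requires both staining and mutation detection, and says only that the technique might become a tool in the work-up. This stands in part. A reader might infer that the protocol claims the stain alone rules out other causes; the documents do not say that. But the endpoint is still worded as suitability for diagnosis, and staining's share of that rests on a comparison with healthy people.

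**No illness effect is shown.** This stands. No section reports that lung, marrow or liver disease raises nasal telomere damage, and the Introduction presents damaged telomeres as characteristic of telomeropathy cells. The worry is stronger for SA-β-Gal, a general senescence marker, than for FISH/IF. The percentages above show a possibility and do not measure it.

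**The data will exist anyway.** Mostly true: section 2.2.2 takes blood and a brushing from each patient. That makes the fix cheap, but it does not supply the missing rule. Unless the classification is fixed before staining is analysed, the result under test can influence it.

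**The sequencing rules may be compatible.** Section 3.2 sequences the stored nasal cells only once suspicion is confirmed. Section 13 calls genetic analysis standard of care on suspicion. Section 5 lets patients refuse it. The first may concern only the stored aliquot, and the sample-flow figure is not visible in the text reviewed. So this is a point to clarify, not a demonstrated contradiction.

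**Conclusion.** The concern holds in limited form and should be fixed. As written, the staining comparison can show that damage and senescence are detectable in patients. It cannot by itself show that staining separates telomeropathy from the same disease with another cause, and no contrast among patients is prespecified.

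Two stronger readings are not supported. One is that the healthy-control comparison is wrong: it is a sound first step, and the controls supply the age reference. The other is that illness is known to bias the stain: its effect is unknown, and the 12% to 87% range follows entirely from assumed shifts of 0.1 to 0.4 SD. The loss of specificity from 85% to between 80% and 74% applies only if a cut-off were taken from healthy controls and the shift were 0.2 to 0.4 SD.

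**What to change.** 1. Before the staining is analysed, and without using it, classify patients as confirmed, not confirmed or indeterminate. Use blood Flow-FISH plus any available genetic result. For the age reference, the Introduction reports that the laboratory "measured TL in a cohort of 491 healthy volunteers aged 0-99 years". State beforehand which group takes patients with no genetic result.
2. Prespecify a confirmed versus not-confirmed contrast among patients, separately for FISH/IF and SA-β-Gal, adjusted for age and presenting diagnosis (lung, marrow, liver). Report sensitivity, specificity and ROC with confidence intervals, and place indeterminate patients in each group in turn. Adjustment for diagnosis does not remove differences in severity or treatment within a diagnosis; say so in the report.
3. Keep patients versus controls as the first step and the controls as the age reference, but do not base a claim of diagnostic suitability for staining on that comparison alone.
4. Report stain-positive, reference-negative patients separately. The Introduction presents FISH/IF as "One way to evaluate telomere dysfunction, independently of TL measurement in blood cells by FF", so some of these may be true cases that the reference missed.
5. State which patients will have a genetic result and reconcile sections 3.2, 5 and 13, checking against the sample-flow figure. Require no extra sequencing.

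**Cost.** A written reference rule and an analysis section, with no added participants, brushings or sequencing. The downsides are fewer cases and wider intervals than in the pooled comparison, and an imperfect reference. If few patients have a genetic result, more will be indeterminate or rest on Flow-FISH alone.

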2. OUTLINE OF OBJECTIVES AND PROJECT DESIGN

2.1 OBJECTIVES

The main objective of this study is to develop new tools for the diagnosis and understanding of telomeropathies. Our more specific aims are:

- To assess the suitability of nasal brushing analyses and blood tests for the diagnosis of telomeropathies
- To assess whether primary cell cultures obtained from nasal brushing could constitute a valuable tool for functional studies of new germline mutations

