3.2. NASAL BRUSHINGS

The nasal brushings will be performed by Prof. [name] or [name], trained ENT specialists, during their scientific time. For patients and controls recruited among patients from the clinic, nasal brushings will be performed while these subjects are at the clinic for their standard cares. For controls recruited outside the clinic, the nasal brushing will require a specific study consultation.

A local vasoconstrictor (Xylometazolin, 1mg/ml) will be applied at the level of the head of the inferior turbinate with the use of a nasal tampon to facilitate the visibility and the access to the olfactory cleft. Each nostril will be assessed, using a 30° rigid endoscope of 4mm (Karl Storz[®], Tuttlingen, Germany), in order to identify the nostril having the most accessible olfactory cleft. This nostril will be chosen to receive the brushing. A sterile disposable cytology brush (i.e. FLOQSwabs, Copan[®], Italy) will be gently rolled on the mucosal surface, at the level of the head of the middle turbinate, as described previously (Orrù et al., 2014). Two brushings will be done for each subject. The brush will then be immerged in a conical centrifuge tube containing DMEM-F12 medium supplemented with GlutaMAX. Cellular material will then be dissociated from the brush using disposable micropipette tips.

In the patients group, cellular material will be split into three parts for specific processing. A first part will be cultured (Prof [name]' lab, de Duve Institute) (Endpoint #2), a second one will be processed by Cytospin for future stainings (Endpoint #1) (Prof [name]' lab, de Duve Institute) and the last part will be kept frozen and further used for whole exome sequencing (Endpoint #1), if the suspicion of telomeropathy has been confirmed. This latter step will be performed at the laboratory of genetics of CUSL (Prof. [name]) In the control group, cellular material will be exclusively used for the staining evaluating the degree of senescence and damages to telomeres.

A Figure is enclosed to this document to summarize experimental procedures and samples flow.

Figure summarizing experimental procedures and samples flow in patients (A) and controls (B)

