9. DATA ANALYSIS

Blood samples collected at CUSL will be analyzed at the laboratory of the Cliniques universitaires Saint-Luc, where leukocyte telomere length will be analyzed using a validated Flow-FISH technique (Prof. [name], head of biologogical hematology department), developed by Prof [name] (UCLouvain).

Cellular material harvested through the nasal brushing will be processed at the laboratory of Prof. [name] (UCLouvain) and at the laboratory of Genetics of CUSL (Prof. [name]).

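### Staining part of Endpoint #1: a patient-versus-control difference alone cannot show diagnostic usefulness, so plan per-subject accuracy by confirmed status

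*Combined protocol and SAP*

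**What the plan says.** Section 2.1 sets a diagnostic aim, "To assess the suitability of nasal brushing analyses and blood tests for the diagnosis of telomeropathies", and section 2.2.2 repeats it as Endpoint #1. For the staining of brushed cells (damaged telomeres and senescence), the Assessments text of section 2.2.2 reads: "We will evaluate if it is possible to detect damaged telomeres and premature cellular senescence in patient, in comparison to healthy controls". The rationale above it says that the investigators "will compare their nasal brushing results to those of age-matched healthy controls".

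Section 2.2 plans 150 patients and 100 controls. The patients are "150 subjects with confirmed or suspected telomeropathy" (section 2.2.1), and the comparator is stated as "100 age-matched healthy controls will be recruited from CUSL". Section 3.2 limits what controls contribute: "In the control group, cellular material will be exclusively used for the staining evaluating the degree of senescence and damages to telomeres".

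Section 9 (Data Analysis) says where material goes, for example "Cellular material harvested through the nasal brushing will be processed at the laboratory", and stops there. No section gives a positivity cut-off, sensitivity, specificity, AUC, reference diagnosis, statistical test or success criterion for the staining.

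**The concern.** Suitability for diagnosis is a question about the individual: does this patient's stain fall outside what is seen in people of the same age without the disease? Whether patients differ from controls on average is another question. With 250 subjects, an average difference reaches significance well before the two distributions separate enough to classify anyone.

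The rationale in section 2.2.2 says that, if brushing detects damaged telomeres and senescence and also identifies mutations, it could become a clinical tool for the diagnostic work-up. The Introduction goes further and proposes it in place of skin biopsy. If the staining half of that condition were judged met on a significant group difference, the support for clinical use would come from a measure that does not describe classification.

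**Working it through.** The plan gives 150 and 100 without a calculation, so it has no figure of its own to reproduce.

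**Inputs.**
- Group sizes 150 and 100: section 2.2.
- Two-sided 5% and 80% power (90% also shown): assumed, not in the documents.
- Normal readouts with equal SD, differences d in SD units: assumed.
- No unusable brushings: assumed.
- Share of the 150 who truly have a telomeropathy: not stated, varied in step 3.

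**Step 1: what the group comparison detects.** SE = √(1/150 + 1/100) = 0.1291. Detectable d at 80% power = (1.960 + 0.842) × 0.1291 = 0.362. A simulation of 20,000 t-tests at this d gave 79.1% power.

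**Step 2: what that difference means for individuals.** Power = Φ(d/0.1291 − 1.960). AUC = Φ(d/√2). Share of the patient group above the controls' 95th centile = Φ(d − 1.645).

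| d (SD) | Power | AUC | Share above control 95th centile |
|---|---|---|---|
| 0.25 (just significant if observed) | 50% | 0.57 | 8% |
| 0.36 | 80% | 0.60 | 10% |
| 0.42 | 90% | 0.62 | 11% |
| 0.50 | 97% | 0.64 | 13% |
| 1.00 | >99.9% | 0.76 | 26% |
| 2.49 | >99.9% | 0.96 | 80% |

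The last row is the separation needed for an illustrative 80% sensitivity at 95% specificity: 0.842 + 1.645 = 2.49 SD, about 7 times 0.36. From 1 SD upwards power is practically 100%, so significance does not tell a weak stain from a good one.

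**Step 3: why confirmed status must enter.** Suppose 20% of patients are affected, the stain separates them perfectly, and the other 80% resemble controls. Then:
- patient-versus-control AUC = 0.20 × 1 + 0.80 × 0.50 = 0.60;
- share above the cut-off = 0.20 × 1 + 0.80 × 0.05 = 24%.

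A perfect stain here gives the same AUC as the 0.36 SD shift in step 2. With 50% affected, its AUC is 0.50 × 1 + 0.50 × 0.50 = 0.75. Accuracy measures on the undivided patient group would therefore mislead too.

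**Step 4: precision of the right measure (Wilson 95% intervals).** For an observed sensitivity of 80%:

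| Confirmed cases | Positive | 95% interval |
|---|---|---|
| 15 | 12 | 54.8% to 93.0% |
| 30 | 24 | 62.7% to 90.5% |
| 75 | 60 | 69.6% to 87.5% |
| 150 | 120 | 72.9% to 85.6% |

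For specificity, 95/100 gives 88.8% to 97.8%. However, a cut-off at the controls' own 95th centile yields 95/100 by construction. That interval shows only the order of precision; an honest estimate needs cross-validation.

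**The case against.** **No group test is written down.** Section 2.2.2 would also fit reading each patient against a control reference range. A reader might infer that the plan specifies a wrong analysis; it does not. What stands is that neither section 2.2.2 nor section 9 describes an individual-level reading, so a bare significant difference could be reported as detection.

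**The 10% is a minimum-effect illustration.** The documents give no effect size, and the Introduction treats damaged telomeres as a consistent feature of telomeropathy patients' cells, which does not suggest a marginal shift. A reader might infer that brushing would miss nine patients in ten. The documents do not support that: the true separation may be large, and a suspected patient below the cut-off may be truly negative.

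**Endpoint #1 is wider than the staining.** It includes blood tests and mutation identification, the latter read patient by patient, and the rationale makes clinical use conditional on both the staining and the mutation result. A reader might infer that the whole endpoint cannot show suitability; the argument does not reach that far. It also does not follow that mutation results can vouch for the stain. Section 3.2 sequences brushed cells only once the suspicion is confirmed, and never in controls.

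**This is early tool development.** A patient-control contrast is a legitimate first step, and the same data allow accuracy measures later. That lowers the severity. It does not remove the case for fixing the cut-off rule and the measures in advance, because cut-offs chosen after seeing the data give optimistic accuracy.

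**Conclusion.** The point holds for the staining part of Endpoint #1. The aim is diagnostic, the only evaluation described is patients against healthy controls, and a significant difference on that comparison would not by itself show that the stain is useful for diagnosis. Under the stated assumptions, a difference detectable with 80% power corresponds to an AUC of 0.60 with about 10% of the patient group above the controls' 95th centile. At 1 SD, where significance is almost certain, the share is still only 26%. These figures rest on assumed error rates and normal, equal-SD readouts; they show the size of the gap and are not a forecast.

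The design can supply the needed measures, but only once confirmed and merely suspected patients are separated. This should be fixed, as a cheap improvement, and is not grounds for holding up the study.

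**What to change.** Amend sections 2.2.2 and 9 before staining results are compared between groups:

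- Define one value per subject for each stain (for example, the share of cells with damaged telomeres and the share positive for SA-β-Gal), with the subject, not the cell, as the unit.
- Set an age-adjusted cut-off for each stain from controls only, because premature means high for age.
- Define confirmed telomeropathy by Flow-FISH and/or genetics, independently of the brushing stain. Section 3.2 already makes sequencing depend on confirmation but does not say how it is established.
- Report sensitivity and AUC, with intervals, in confirmed patients.
- Report the proportion positive separately in suspected but unconfirmed patients, and do not call it sensitivity.
- Report cross-validated specificity in controls, described as specificity against healthy people only.
- Base any claim that the staining is suitable on these measures, and keep the group difference as descriptive.

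The cost is wording, with no new samples or subjects. The downsides are wider intervals, since sensitivity rests on an unstated number of confirmed cases, some precision lost to age modelling with 100 controls who include children and adults, and a headline that is harder to meet than a significant p-value.
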